7.8.3 Pharmacodynamic Analyses

All PD data will be listed and summarized by treatment, where appropriate. The comparison of the concentration of B-cell kinetics between CT-P10, Rituxan and MabThera will be performed using ANCOVA, with treatment as a fixed effect and baseline values, country, gender, race, prior anti-TNF- α blocker status(inadequate response versus intolerant case), and RF or anti-CCP status (both positive versus both negative versus either RF or anti-CCP negative) fitted as covariates. If country is found to be unsuitable as a covariate due to the number of levels, then this may be pooled into a new variable, region defined in SAP, for use as a covariate. Point estimates and 95% CIs will be provided. Pharmacodynamic data will also be summarized using quantitative descriptive statistics (including geometric mean and CV, where appropriate).

7.8.4 Safety Analyses

The safety analysis will be performed on the safety population by presenting data on hypersensitivity monitoring via vital sign measurements (including blood pressure, heart and respiratory rates, and temperature), immunogenicity testing, immunoglobulin (IgM, IgG and IgA) testing, vital sign measurements, ECGs, signs and symptoms of TB monitored throughout the study, physical examination findings, AEs, infections, IRRs, clinical laboratory analyses, pregnancy testing, and concomitant medications.

All safety data will be listed and summarized by treatment as appropriate.

7.8.4.1 Demographic, Baseline, and Background Characteristics

Demographics (age, gender, race, and etc.) and baseline and background characteristics will be presented in summary tables. Qualitative data (e.g., medical history) will be summarized in contingency tables, and quantitative data (e.g., age) will be summarized using quantitative descriptive statistics.

7.8.4.2 Adverse Events

Adverse events will be coded to system organ class (SOC) and preferred term (PT) according to MedDRA. Adverse events will be graded for severity according to the CTCAE v4.0.

The following AE summaries will be reported by SOC, PT, and treatment:

- Number and percentage of patients reporting at least 1 AE
- Number and percentage of patients reporting at least 1 SAE
- Number and percentage of patients discontinuing the study drug due to an AE
- Number and percentage of patients with AEs of special interest (infusion-related AEs and infections)

If more than 1 AE is recorded for a patient within any SOC or PT, the patient will be counted only once within the respective summary.

Adverse events will also be summarized by maximum intensity and relationship to study drug with the percentage of patients in each category. If more than 1 AE is recorded for a patient within any SOC or PT, the patient will only be counted once using the most severe assessment.

Adverse events of special interest will also be summarized by intensity.

7.8.4.3 Laboratory Test Analyses

Clinical laboratory tests (hematology, clinical chemistry, and urinalysis) will be summarized, by treatment, at each scheduled collection time. For continuous parameters, change from Baseline will also be summarized for all scheduled collection times after the first infusion. Baseline will be the latest available measurement prior to the first infusion.

All laboratory results will be listed. Additional listings will be provided showing laboratory results outside the normal range.

7.8.4.4 Immunogenicity

All data will be listed and summarized by treatment as appropriate.

7.8.4.5 Immunoglobulin (IgM, IgG and IgA) Values

All data will be listed and summarized by treatment as appropriate.

7.8.4.6 Vital Signs and Weight

Vitals signs (systolic and diastolic blood pressure, heart rate, respiratory rate, and temperature) and weight will be summarized, by treatment, at each scheduled collection time. Change from Baseline will also be summarized for all scheduled collection times after the first infusion for vital signs. Baseline will be the latest available measurement prior to the first infusion.

All data will be listed.

7.8.4.7 Electrocardiograms

Overall assessment and ECG parameters will be summarized, by treatment, at each visit. In addition, change from Baseline in ECG parameters will also be summarized, by treatment. Baseline will be the result at Screening.

All data will be listed.

7.8.5 Missing Data Analysis

In order to evaluate the impact of missing data on the primary endpoint results, additional analyses with missing data imputation will be conducted for primary efficacy endpoint of DAS28 (CRP) in all randomized population. Multiple imputation (MI) with the missing at random (MAR) assumption and last observation carried forward (LOCF) with the missing completely at random (MCAR) assumption will be used for missing data imputation in all randomized population for both CT-P10 and reference (Rituxan and MabThera) groups.

Additionally, tipping point analysis will be conducted for a sensitivity analysis under the missing not at random (MNAR) assumption to identify assumptions (tipping point) under which confidence interval no longer rules out differences in the change from baseline of DAS28 (CRP) for the therapeutic equivalence margin of ± 0.5 .

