7.2 Efficacy Endpoints

7.2.1 Primary Efficacy Endpoint

The following efficacy parameter for the study drug (CT-P10 and reference products) will be determined as the primary efficacy endpoint:

• The change from Baseline in disease activity measured by DAS28 (CRP) at Week 24

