7.6 Analysis Sets

Five patient populations are defined: PK, efficacy, PD, safety, and all-randomized populations.

The PK population is defined to be all patients who receive at least 2 doses (Week 0 and Week 2) of study drug (CT-P10, Rituxan or MabThera), who provide sufficient blood concentration data to compute the required PK variables, and who do not have any major protocol violation including a violation of the inclusion and exclusion of criteria. The PK population will be the primary population for the summary and analysis of PK data.

The efficacy population is defined to be all patients who receive at least 1 dose of study drug (CT-P10, Rituxan or MabThera), who have at least 1 post-treatment efficacy result, and who do not have any major protocol violation including a violation of the inclusion and exclusion of criteria. The efficacy population will be the primary population for the summary of efficacy data.

The PD population is defined to be all patients receiving at least 1 dose of study drug (CT-P10, Rituxan or MabThera) and providing at least 1 post-treatment PD result. The PD population will be the primary population for the summary of PD data.

The safety population is defined to be all patients who receive at least 1 dose (full or partial) of study drug (CT-P10, Rituxan or MabThera). The safety population will be the primary population for the summary of safety data.

The all-randomized population is defined to be all patients enrolled and randomly assigned to receive a dose of study drug, regardless of whether or not any study drug dosing was completed. All efficacy parameters will also be analyzed for the all-randomized population.

The number of patients, who discontinue from the study prematurely, together with the reasons for discontinuation, will be summarized. In addition, for each analysis population the number of patients will be presented.

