7.8.2 Efficacy Analyses

7.8.2.1 Primary Efficacy Analysis

The primary efficacy analysis includes patients from Part 1 and Part 2. The primary analysis for DAS28 is an analysis of covariance (ANCOVA) comparing the change from baseline of DAS28 after 24 weeks of treatment between two treatment groups, CT-P10 and reference products, considering the treatment as a fixed effect and country, gender, race, prior anti-TNF- α blocker status (inadequate response versus intolerant case), and RF or anti-CCP status (both positive versus both negative versus either RF or anti-CCP negative) fitted as covariates. If country is found to be unsuitable as a covariate due to the number of levels, then this may be pooled into a new variable, region defined in the SAP, for use as a covariate.

Similarity for the change from baseline of DAS28 (CRP) at week 24 will be evaluated based on the two-sided 90% confidence interval obtained from the ANCOVA model for the difference of means of the change in DAS28 (CRP) between the two treatment groups. The equivalence margin for the 90% CI is defined as [-0.50, 0.50].

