### **5.8. Missing Values and Outliers**

In order to evaluate the impact of missing data on the efficacy primary endpoint results, additional analyses with missing data imputation will be conducted for the primary efficacy endpoint of DAS28 (CRP) at Week 24 in all-randomized population.

Two imputation methods will be used for sensitivity analysis: Last observation carried forwards (LOCF) and Multiple imputation (MI) with the Missing at random (MAR) assumption. In addition, Tipping point analysis will be conducted based on MI results.

LOCF will impute missing values by the last value observed. MI with the MAR assumption will use regression method to impute missing data. Gender, country (or region), race, baseline value of DAS28 (CRP), prior anti-TNF alpha blocker status (intolerance case versus inadequate response), RF or anti-CCP status (both positive versus both negative versus either RF or anti-CCP negative), study part, treatment group and interaction of treatment group with study part will be used as regression covariates. 10 imputed datasets will be created by multiple imputations, and results from these 10 datasets will be pooled.

LOCF and MI with the MAR results will be provided displaying descriptive statistics for actual value and change from baseline in DAS28 (CRP) at Week 24. Additional, ANCOVA for the DAS 28 (CRP) will be conducted along with its 90% CI between CT-P10 and Reference products treatment group.

Tipping point analyses will be conducted under MNAR (Missing Not at Random) scenarios. Imputed values will be shifted gradually from the imputed values by MI, by treatment groups (CT-P10 versus combined Rituxan and MabThera group) to make MNAR scenarios. A point estimate and 90% confidence interval (CI) for the treatment difference will also be calculated using an analysis of covariance (ANCOVA) considering the treatment as a fixed effect and gender, country (or region), race, study part, interaction of treatment group with study part, prior anti-TNF- $\alpha$  blocker status (intolerance case versus inadequate response), and RF or anti-CCP status (both positive versus both negative versus either RF or anti-CCP negative) fitted as covariates under these scenarios, and the scenario under which confidence interval no longer

rules out differences in the change from baseline of DAS28 (CRP) at Week 24 for the therapeutic equivalence margin of  $\pm 0.5$  will be displayed.

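### Protocol 7.8.5 ties LOCF to MCAR, but MCAR does not make LOCF valid for the Week 24 change in DAS28 (CRP)

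*Protocol*

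**What the plan says.** The primary endpoint in Protocol 7.2.1 is "The change from Baseline in disease activity measured by DAS28 (CRP) at Week 24". It is analysed by ANCOVA, with a 90% CI compared with ±0.50 (Protocol 7.8.2.1). The efficacy population is primary (Protocol 7.6).

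For missing data, Protocol 7.8.5 adds three analyses in the all-randomized population:
- multiple imputation (MI) under MAR;
- LOCF, described as "last observation carried forward (LOCF) with the missing completely at random (MCAR) assumption will be used for missing data imputation in all randomized population";
- a tipping-point analysis under MNAR.

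SAP 5.8 calls LOCF and MI sensitivity analyses and does not repeat the MCAR label. Its rule is that "LOCF will impute missing values by the last value observed". It does not say whether a baseline or EOS value may be carried. For the imputed data, an "ANCOVA for the DAS 28 (CRP) will be conducted along with its 90% CI between CT-P10 and Reference products treatment group". The SAP then adds that "Tipping point analyses will be conducted under MNAR (Missing Not at Random) scenarios", starting from the MI results.

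SAP 11.2 separately runs the Week 24 ANCOVA in the all-randomized population, with no imputation stated.

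**The concern.** MCAR says that the patients who leave are a random sample. It does not say that a value from an earlier visit stands in for Week 24. LOCF needs that second condition: no mean change after the last observation. DAS28 is scheduled at Weeks 4, 8, 12, 16, 20 and 24 after infusions at Weeks 0 and 2 (Protocol Table 4). A patient last seen early may not have reached the Week 24 response, and neither document gives a DAS28 time course to show otherwise.

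The LOCF ANCOVA yields a 90% CI that will be read beside the equivalence margin. Under exactly the assumption that the protocol names, it can show a difference between identical products, or shrink a real one. A reader who trusts the label would take it as a check that is sound under MCAR. It is not, unless response has levelled off.

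**Working it through.** **1. The plan's own figure.** Protocol 7.5 gives 133 and 189 evaluable patients, SD 1.32, margin 0.50 and a 90% CI. I assume a true difference of 0.
- SE = 1.32 × √(1/133 + 1/189) = 0.1494.
- Power = 2Φ(0.50/0.1494 − 1.645) − 1 = 91.1%.

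The stated 90% or so reproduces. LOCF does not enter it.

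**2. LOCF mean under MCAR.** Let μ be the mean Week 24 change, d the drop-out proportion, and s the average share of μ not yet reached at the last observed visit. Then

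LOCF mean = μ × (1 − d × s).

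The bias is zero only if s = 0.

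**3. Assumptions not in the documents.** μ = −2.0. Last visits are spread evenly over Weeks 4 to 20. The share of the change reached at Weeks 4, 8, 12, 16 and 20 is
- concave: 40, 65, 80, 90, 97%; mean 74.4%, so s = 0.256;
- linear: 1/6 to 5/6; mean 50%, so s = 0.50.

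**4. Identical products.** The false difference is (difference in drop-out) × 2.0 × s.
- Equal drop-out: 0.
- 15% against 5%: 0.10 × 2.0 × 0.256 = 0.051 (concave); 0.10 × 2.0 × 0.50 = 0.10 (linear).

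**5. EOS visits.** Withdrawn patients should, where possible, be assessed at least 8 weeks after the last infusion (Protocol 4.2.2). After the Week 2 infusion that means Week 10 or later. Suppose every such patient attends and no carried value is earlier than Week 10. The Week 4 and Week 8 shares both become 72.5% (concave, interpolated) or 10/24 (linear).
- Concave: s = 0.176, false difference 0.10 × 2.0 × 0.176 = 0.035.
- Linear: s = 0.433, false difference 0.10 × 2.0 × 0.433 = 0.087.

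**6. True difference 0.50, equal 10% drop-out.** The difference grows in proportion to response, and all 149 and 212 patients count: SE = 1.32 × √(1/149 + 1/212) = 0.1411.
- Concave: expected estimate 0.50 × (1 − 0.10 × 0.256) = 0.487; pass rate Φ(0.0128/0.1411 − 1.645) = 6.0%.
- Linear: expected estimate 0.50 × (1 − 0.10 × 0.50) = 0.475; pass rate Φ(0.025/0.1411 − 1.645) = 7.1%.

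Simulations of this setting gave 5.6% to 7.2% for LOCF. The analysis of observed Week 24 values stayed at 4.6% to 5.6%.

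**7. True difference 0.50, unequal drop-out.** Take CT-P10 at −1.5 and reference at −2.0.
- 5% CT-P10, 15% reference: 0.50 + (0.075 − 0.30) × s = 0.442 or 0.388, toward similarity; pass rate about 11% or 20%.
- 15% CT-P10, 5% reference: 0.50 + (0.225 − 0.10) × s = 0.532 or 0.563, away from similarity; pass rate about 3% or 2%.

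**8. Whether baseline is carried.** I varied μ from −1.5 to −2.5 and the curve from linear to a plateau at Week 8. The false difference at 15% against 5% runs from 0.012 to 0.125 if only post-baseline values are carried, and from 0.035 to 0.146 if baseline may be. The SAP leaves this choice open, and the all-randomized set can include patients never dosed (SAP 5.4.1).

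**The case against.** **LOCF decides nothing.** The primary analysis does not use it. The all-randomized ANCOVA without imputation, MI under MAR and the tipping point stand beside it, and the SAP has already dropped the MCAR label. All of this stands, so the point concerns one supportive analysis and its stated justification.

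**The effect is small at the planned drop-out.** The documents hypothesize 10% with no difference between groups. Step 6 then gives a shrinkage of 0.01 to 0.03. The larger figures need unequal drop-out, which is assumed. This also stands.

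**EOS values soften the problem.** They do, but step 5 shows that they do not remove it.

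**An MMRM is a preference when MI under MAR is planned.** This stands only in part. The MI covariates listed in SAP 5.8 include no post-baseline DAS28, so LOCF is the only planned missing-data analysis that draws directly on Weeks 4 to 20. Lack of efficacy and disease progression are listed reasons for withdrawal (Protocol 4.2.1), so those visits carry information.

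Two stronger readings are tempting, and neither is supported:
- *LOCF systematically favours similarity.* Step 7 shows that it can go either way.
- *The LOCF standard error is too small because imputed values count as observed.* Each patient contributes one independent value. In simulation the average standard error was 0.1425 against a sampling SD of 0.1423. The fault is bias.

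**Conclusion.** The MCAR justification in Protocol 7.8.5 is wrong as written. MCAR must be joined by no mean change after the last visit, and the documents do not justify that.

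Under the assumed curves, the consequence is a false difference of about 0.05 to 0.10 at 15% against 5% drop-out, or 10% to 20% of the margin. It is 0.035 to 0.087 if EOS values from Week 10 onward are carried. With equal 10% drop-out and a true difference at the margin, false equivalence is about 6% to 7%.

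These sizes rest on an assumed Week 24 change, time course and drop-out pattern. There is no bias if response has levelled off before drop-out. A reader might infer that the primary equivalence conclusion or its power is compromised. The documents do not support that, because LOCF enters neither.

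**What to change.** In Protocol 7.8.5 and SAP 5.8:
- Delete the statement that LOCF rests on MCAR.
- Replace the LOCF ANCOVA with an MMRM of DAS28 (CRP) change at Weeks 4 to 24 in the all-randomized population. Include treatment-by-visit, the SAP 11.2 covariates and an unstructured covariance, and report the Week 24 contrast with its 90% CI. It is valid under MCAR and MAR and uses data already collected.
- Name the all-randomized ANCOVA without imputation in SAP 11.2 as the analysis valid under MCAR.
- If LOCF output is kept, label it as assuming no change after the last visit, state whether baseline and EOS values may be carried forward, and do not cite it as support for similarity.

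The cost is revised wording and one extra model, with slightly more programming than LOCF.

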7.8.6 Interim Analyses

Although no formal interim analyses are planned, the sponsor plans to prepare 2 clinical study reports. However, clinical study report(s) can be generated during the Study Period in addition to 2 clinical study reports as planned for regulatory or academic purpose.

- 1. To report data for each patient up to Week 24
- 2. To report data after completion of study (including safety laboratory [B-cell, IgM and IgG] follow-up closed)

7.9 Data Quality Assurance

Steps to be taken to ensure the accuracy and reliability of data include the selection of qualified investigators and appropriate study centers, review of protocol procedures with the investigator and associated personnel before the study, periodic monitoring visits by CELLTRION, Inc. or its designee, and direct transmission of clinical laboratory data from a central laboratory into the clinical database. The eCRF will be reviewed for accuracy and completeness by the monitor during on-site monitoring visits and after their return to CELLTRION, Inc. or its designee; any discrepancies will be resolved with the investigator or designees, as appropriate. The data will be entered into the clinical study database and verified for accuracy.

Quality assurance personnel from CELLTRION, Inc. or its designee may visit the study center to carry out an audit of the study in compliance with regulatory guidelines and company policy. Such audits will require access to all study records, including source Protocol Version 5.1, including Country-Specific Protocol Amendment 1 (US) – 01 April 2016 Pa

Page 86

documents, for inspection and comparison with the eCRF. Patient privacy must, however, be respected. Sufficient prior notice will be provided to allow the investigator to prepare properly for the audit.

Similar auditing procedures may also be conducted by agents of any regulatory body reviewing the results of this study in support of a licensing application. The investigator should immediately notify CELLTRION, Inc. or its designee if they have been contacted by a regulatory agency concerning an upcoming inspection.

8 Ethics

8.1 Independent Ethics Committee or Institution Review Board

Federal regulations and the ICH guidelines require that approval be obtained from an IRB/IEC before participation of human patients in research studies. Before study onset, the protocol, informed consent, advertisements to be used for the recruitment of study patients, and any other written information regarding this study to be provided to the patient or the patient's legal guardian must be approved by the IRB/IEC. Documentation of all IRB/IEC approvals and of the IRB/IEC compliance with ICH harmonised tripartite guideline E6(R1): Good Clinical Practice (GCP) will be maintained by the study center and will be available for review by the sponsor or its designee.

All IRB/IEC approvals should be signed by the IRB/IEC chairman or designee and must identify the IRB/IEC name and address, the clinical protocol by title or protocol number or both, and the date approval or a favorable opinion was granted.

The investigator is responsible for obtaining continued review of the clinical research at intervals not exceeding 1 year or otherwise specified by the IRB/IEC. The investigator must supply the sponsor or its designee with written documentation of continued review of the clinical research.

8.2 Ethical Conduct of the Study

The study will be performed in accordance with the ethical principles that have their origin in the Declaration of Helsinki, ICH GCP, and all applicable regulations.

8.3 Patient Information and Consent

A written ICF in compliance with regulatory authority regulations or US Title 21 Code of Federal Regulations (CFR) Part 50 shall be obtained from each patient before entering the study or performing any unusual or nonroutine procedure that involves risk to the patient. An informed consent template may be provided by the sponsor to investigative study centers. If any institution-specific modifications to study-related procedures are proposed or made by the study center, the consent should be reviewed by the sponsor or its designee or both before IRB/IEC submission. Once reviewed, the consent will be submitted by the investigator to his or her IRB/IEC for review and approval before the start of the study. If the ICF is revised during the course of the study, all active participating patients must sign the revised form.

Page 88

Before recruitment and enrollment, each prospective patient or his or her legal guardian will be given a full explanation of the study and be allowed to read the approved ICF. Once the investigator is assured that the patient/legal guardian understands the implications of participating in the study, the patient/legal guardian will be asked to give consent to participate in the study by signing the ICF.

The investigator shall retain the signed original ICF(s) and give a copy of the signed original form to the patient or legal guardian.

9 Investigator's Obligations

The following administrative items are meant to guide the investigator in the conduct of the study but may be subject to change based on industry and government standard operating procedures, working practice documents, or guidelines. Changes will be reported to the IRB/ IEC but will not result in protocol amendments.

